5.1. Analysis of primary outcome

The log-transformed 24-hour proteinuria values will be analyzed by a mixed-effects general linear regression model with treatment and period as fixed factor and patients (nested in sequence) as a random factor. This type of model, which accounts for repeated observations within individuals (measurement occasion at level one, individuals at level two) will allow us to estimate the treatment effect (estimated by restricted maximum likelihood). We will also explore the period-specific treatment effect adding in the model the interaction between the treatment and period covariates. If the baseline characteristics will be considerably different across the three regions included (Malaysia, North America, Europe) we shall consider to include region as a layer in the multilevel model fitted or as fixed effect covariate. We will also analyse the log-transformed 24-hour albuminuria values (a specific protein using the same model as described above).

The change in secondary outcomes, mGFR, eGFR, body weight and systolic blood pressure will be analyzed by the same model as showed for the proteinuria outcome.

In general, the models employed will be:

$$y_{it} = \beta_{0i} + \beta_1 Treat_{it} + \beta_2 Period_{it} + \beta_3 Interaction + \varepsilon_{it}$$

$$\beta_{0i} = \beta_0 + u_{0i}$$

$$\varepsilon_{it} \sim N(0, \sigma_\varepsilon^2)$$

Where y_{it} is the outcome for the individual i at time point t , β_{0i} is the intercept for individual i comprised of a sample-average fixed effect β_0 and an individual effect u_{0i} and ε_{it} is the residual error.

Complete case analyses, that is analysing records that present the whole set of information (outcome and covariates) for every visit of the patients will be performed. Patterns of missing data (for the outcomes and the covariates) will be reported. If the proportion of missing records is higher than 5% and/or we will suspect of particular missing mechanisms we will impute the missing values by multiple imputation using the full conditional specification.

Further, if there will be baseline measurements that are missing we will use the values measured at the screening visit: we will document the frequency of this imputation.

As a complementary analysis we will also include week 3 (mid-period 1 visit) and week 15 (mid-period 2 visit) data points so to explore potential “immediate” treatment effects: this will be done for the primary outcome and the secondary outcomes for which the data is available (for instance, no eGFR is collected at week 3 and 15).

A fully-adjusted model will be also considered for the primary outcome including – among the others – the following time-varying variables: mGFR, systolic blood pressure, body weight and Hba1c.

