2. OBJECTIVES

Primary Objective:

- To assess the change from baseline in 24-hr proteinuria with dapagliflozin for six weeks relative to placebo treatment in patients with non-diabetic kidney disease and proteinuria > 500 mg/day on stable ACEi or ARB treatment.

Secondary Objectives

- To assess the effect of dapagliflozin 10 mg/d compared to placebo on Glomerular Filtration Rate (GFR) using iothexol clearance
- To assess the effect of dapagliflozin 10 mg/d compared to placebo on systolic/diastolic blood pressure
- To assess the effect of dapagliflozin 10 mg/d compared to placebo on body weight
- To assess the effect of dapagliflozin 10 mg/d compared to placebo on selected neurohormones/biomarkers:
 - Hormones of the RAAS (plasma and urine)
 - Natriuretic peptides
 - Urinary adenosine
 - Co-peptin
 - Immunoglobulin G (plasma and urine)
- To characterize the safety of dapagliflozin vs. placebo by determining the number of hypoglycemia episodes between groups and serious adverse events.

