Potentially eligible subjects who complete the screening visit will enter the run-in period if they are not using an ACEi or ARB, or if they are not using a maximum tolerated dose of an ACEi or ARB. During the run-in period, ACEi or ARB will be started or uptitrated towards the maximum tolerated antihypertensive dose. If a patient does not tolerate the maximum dose of an ACEi or ARB, this should be documented in the eCRF and the patient can proceed to the double blind treatment period if all other entry criteria are met.

Visit 1

Subjects who entered the run-in period will return for the run-in visit 4 weeks after starting an ACEi/ARB or after ACEi/ARB dose adjustments. The subject has to be on a stable dose of an ACEi or ARB for at least 4 weeks before randomisation. More visits may be required to make sure that the subject still meet all entry criteria at the end of the run-in period. The run-in period may take up to a maximum of 16 weeks. If the eGFR remains ≥ 25 ml/min/1.73m² and the proteinuria level remains between 500 mg/24hr and ≤ 3500 mg/24hr at the end of the run-in period, the patient qualifies to proceed to the double blind treatment period.

Double-Blind Treatment Period:

Eligible subjects will enter in the randomized, double-blind, treatment period if their ACEi/ARB and diuretic medication is stable for at least 4 weeks and all entry criteria are met. The

randomization codes generated by University Medical Center Groningen will be programmed into the IBM Clinical Development Merge to randomly assign subjects to a treatment arm. The investigational drug will be dispensed by the principal investigator or delegated based on the randomization number.

Subjects will continue to maintain their stable doses of commercially available ACEI or ARB, and diuretics if applicable, throughout the double blind phase. Patients will be counseled to maintain a stable habitual dietary salt intake

Visit 2

The randomization visit procedures should be completed on a single day. The randomization visit procedures will include GFR measurement by plasma clearance of nonradioactive iohexol after a single intravenous dose. The GFR measurement will last approximately 4 hours for patients. The first dose of blinded study medication should only be administered on Day 1 AFTER ALL randomization visit procedures have been completed. Patient will be treated in random order with dapagliflozin 10 mg QD or matching placebo QD.

Visit 3, 4, and 5

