3.4 Sample size calculation

With a sample size of 50 patients completing the study and assuming a conservative standard deviation of 0.7 in log transformed proteinuria (within-subject standard deviation of 0.475), the trial will have 80% power to detect a mean reduction in albuminuria of 25% (i.e, $\delta=0.288$ on the log-transformed proteinuria scale) or more with dapagliflozin compared to placebo (alpha 0.05). This calculation is based on individual patient data from various clinical trials on the anti-proteinuric effects of different agents in diabetes and non-diabetes trials for which we have the individual patient data including ROAD, RENAAL and IDNT trials. For calculation of the sample size, the percent change in proteinuria is log-transformed to take into account the skewed distribution of proteinuria. Under the assumption that no carry-over effects and no period effects occur, a paired-t-

test is deemed appropriate to calculate the sample size. Using these assumptions, we calculate that 50 patients completing the study will provide 80% power to detect a 25% reduction in albuminuria. Assuming that approximately 5% of patients will discontinue the study prematurely, we intend to enrol 53 subjects.

We believe a reduction of >25% with dapagliflozin versus placebo can be detected. We recently published a large analysis of patients with diabetes and demonstrated that dapagliflozin decreased proteinuria by 33%. Trials with other SGLT2 inhibitors have also documented proteinuria reductions of approximately 30%.

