4.2. Randomization and blinding

Treatment sequence of dapagliflozin and placebo will be randomized. A computer generated randomized code generated by the sponsor will be used. The pharmacy of each participating centre will store the randomization code. Unblinding is not to be performed for any reason, other than an emergency where unblinding is required.

5. Statistical analysis

The flow of patients through the study (screened, fulfilled eligibility criteria, excluded, randomized and potential drop-outs) will be graphically displayed in a CONSORT diagram. Baseline characteristics will be described by sequence group. All tests are to be two-sided with nominal level alpha set at 5%.

Descriptive statistics will be used to analyse the means and distribution between all the study variables. The means of the normal distributed variables will be compared with the student T-test and non-parametric tests (Mann-Whitney U-test for continuous and Chi-Square test for categorical variables) will be used for the variables that present a particularly skewed distribution.

The base-case analyses of the treatment effects will be unadjusted (with the exception of the period effect).

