5.2. Subgroup and sensitivity analyses

The primary and secondary outcomes will be analyzed in the following subgroups:

1. Age (\geq or $<$ 60 years or median)
2. Gender (Male / Female)
3. Region (Asia, Europe, North Am)
4. Proteinuria (\geq or $<$ 1000 mg/24hr)
5. mGFR (\geq or $<$ 45 ml/min/1.73m² or median)
6. Systolic blood pressure (\geq or $<$ 130 mmHg or median)
7. Body mass index (\geq or $<$ 25 kg/m² or median)
8. Kidney Diagnosis
9. Diuretic use (Yes/No)

We will flag patients who have started or changed the dose of any medication that may influence the primary outcome (e.g. NSAID, corticosteroids, diuretic treatment, mineralocorticoid receptor antagonists, and Vitamin D during the double blind treatment periods and perform a sensitivity analysis on the primary outcome excluding them.

Another sensitivity analysis will be performed on the primary outcome where we will use the average of the screening and randomization 24-hr proteinuria value.

All the analyses described in the SAP are based on the intention to treat principle (that is, patients analysed according to the group they were originally assigned). We will also perform the analyses on the primary outcome(s) considering “on treatment” patients defined as those with adherence to study medication \geq 80% (as determined by pill count).

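### Filling a missing baseline with the screening value gives run-in patients a baseline that predates their stable ACEi/ARB dose, which distorts within-treatment changes from baseline

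*SAP*

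**What the plan says.** The primary objective (Protocol section 2, SAP 2.1) is change from baseline in 24-hour proteinuria in patients with "proteinuria > 500 mg/day on stable ACEi or ARB treatment".

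For missing baselines, SAP 5.1 states: "Further, if there will be baseline measurements that are missing we will use the values measured at the screening visit". The only safeguard is a promise to document how often this happens. The rule does not separate run-in patients from those randomized directly, and does not say whether it covers the week-0 baseline, the week-12 baseline or both.

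Protocol section 3 (Run-in Period) places the run-in after screening: "During the run-in period, ACEi or ARB will be started or uptitrated towards the maximum tolerated antihypertensive dose". Under Visit 1 it adds: "The run-in period may take up to a maximum of 16 weeks". Visit 1 falls 4 weeks after the start or adjustment, further visits are allowed, and eGFR and proteinuria are checked again before randomization. The Time and Events Table schedules a 24-hour urine, vital signs and blood at the run-in visit. The list of urine collections in SAP 4.1 omits that visit.

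In SAP 5.2, one sensitivity analysis of the primary outcome changes the baseline: "we will use the average of the screening and randomization 24-hr proteinuria value".

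**The concern.** For a run-in patient, the screening and randomization values come from different background therapy. If the randomization value is missing and the screening value takes its place, any fall in proteinuria produced by the ACEi/ARB during run-in appears as a fall on whichever study treatment follows.

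The outputs exposed are the change-from-baseline rows in SAP Tables 6 to 8 and the proportions with a 30%, 40% or 50% reduction in SAP 5.3, if those are taken from baseline. If the rule also covers week 12, a period-2 baseline would be filled with a value from before period 1. That value would be at least 12 weeks old, and about 28 weeks old after a 16-week run-in (16 + 12).

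The averaging analysis in SAP 5.2 needs no missing data. It brings the pre-run-in value into every patient whose therapy changed after screening, so it cannot serve as a check on this problem.

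**Working it through.** **Design figures.** Protocol 3.4 states that "50 patients completing the study will provide 80% power to detect a 25% reduction in albuminuria", "assuming a conservative standard deviation of 0.7 in log transformed proteinuria (within-subject standard deviation of 0.475"), with delta 0.288 = -ln(0.75). SAP section 5 sets two-sided alpha at 5%. A paired t-test with n = 50, SD of the difference 0.7 and delta 0.288 gives 81.4% power (49 patients for 80%). With SD 0.475 × √2 = 0.672, power is 84.4% (45 patients). Also 50/0.95 = 52.6, so 53 enrolled. The design figures reproduce and are not in dispute; delta is the yardstick below.

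**Assumption.** The documents give no run-in effect on proteinuria. Take a reduction r of 20%, 30% or 40%.

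**Per affected patient** (run-in and baseline missing). Spurious log change = ln(1 - r).

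| r | log change | multiple of 0.288 |
|---|---|---|
| 20% | -0.223 | 0.77 |
| 30% | -0.357 | 1.24 |
| 40% | -0.511 | 1.77 |

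**Mean change in one treatment's column**, assuming 5 of 50 affected: 5 × ln(1 - r)/50 = -0.022, -0.036, -0.051, which is 8%, 12% and 18% of delta.

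**Proportion with a 30% reduction, no true effect.** Take the SD of a change as 0.475 × √2 = 0.672.

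- Sound baseline: Φ(ln 0.7/0.672) = 29.8%.
- Affected patient: Φ((ln 0.7 - ln(1 - r))/0.672) = 42.1%, 50.0%, 59.1%.
- Whole column, 5 of 50 affected: 0.9 × 29.8% + 0.1 × (42.1% to 59.1%) = 31.0% to 32.7%.

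If 0.475 is instead read as the SD of a change, the same formulas give 22.6% with sound baselines and 24.3% to 26.6% for the column. The rise is still about 2 to 4 percentage points.

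**Treatment difference.** Simulation of 4,000 trials of 50 patients, analysing change from each period's baseline, with half the patients via run-in, r = 30%, no true effect, and each change given SD 0.475 so that the period difference has SD 0.672:

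- 10% of baselines missing at random in each period: mean change -0.017 in both columns (by formula 0.5 × 0.10 × 0.357 = 0.018); treatment difference 0.000.
- 20% of period-2 baselines missing in the placebo-dapagliflozin sequence only: difference -0.018 (by formula 0.5 × 0.20 × 0.357/2 = 0.018), which is 6% of delta.

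**Averaging analysis (SAP 5.2).** With an arithmetic mean, the spurious fall from the averaged baseline is 1 - 2/(1/(1 - r) + 1) = 11.1%, 17.6%, 25.0%. If the average is taken on the log scale, it is 1 - √(1 - r) = 10.6%, 16.3%, 22.5%.

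**The case against.** The strongest reply is that the primary estimate may never use the filled value. SAP 5.1 models log proteinuria values on treatment and period with a patient effect. The equation has no baseline term, and SAP section 5 calls the base-case analyses unadjusted apart from period. If only week-6 and week-18 values enter, the fill leaves the model estimate alone and reaches only the change tables and responder counts. This stands. The SAP does not define the outcome variable closely enough to settle it.

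A reader might infer that the rule inflates the estimated dapagliflozin effect. The documents do not support that. Sequence is randomized, period is in the model, and the false change falls on placebo as well. Bias in the difference needs missing baselines that are unbalanced between treatments, and nothing in the documents predicts this. Nor should the 20-40% shift or the 42-59% responder chance be read as trial-level figures or set against the 25% target effect: they describe one affected patient, while the target is a mean over all patients.

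Missing week-0 baselines should also be rare, because a day-1 urine is scheduled and the first dose follows completion of all randomization procedures. That stands, but it does not help the averaging analysis, where no value need be missing. There, a common averaged baseline used in both periods would cancel within patient, and one used in period 1 only would go mainly to the period effect. The within-treatment changes are still shifted.

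Two limits remain. The Protocol's general design text and SAP 4.1 describe the run-in as stabilising a drug changed in the 4 weeks before screening, whereas the Protocol's Run-in Period text describes starting or uptitrating it afterwards. These passages must be reconciled; for patients already changed before screening the shift would be smaller. And iohexol GFR is not scheduled at screening, so the rule cannot operate for measured GFR.

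**Conclusion.** The point holds as a defect of baseline definition. For run-in patients the fill conflicts with the stable-therapy baseline in the primary objective, although the protocol already collects a more suitable value. The consequence is distortion of within-treatment changes in Tables 6 to 8 and of responder proportions taken from baseline. At 5 of 50 affected, that is about -0.02 to -0.05 on the log scale and a rise of roughly 1 to 3 percentage points in the 30% responder proportion (from about 30% to 31-33%). The averaging analysis carries a spurious 11-25% fall in each run-in patient whose therapy changed after screening.

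These sizes rest on the assumed 20-40% run-in effect and, for the fill rule, on an assumed count of affected patients. Whether the rule reaches week 12 is a matter of interpretation that the SAP leaves open. The correction is worth making because it is cheap and removes an avoidable error, not because the main treatment comparison is shown to be unsound.

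**What to change.** In SAP 5.1:

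- For run-in patients, fill a missing week-0 baseline with the last pre-randomization run-in value on the stable ACEi/ARB dose. Do not name Visit 1 as such, since later run-in visits may follow it.
- Use the screening value only for patients randomized directly.
- Do not fill a missing week-12 baseline from screening; handle it by the multiple imputation already planned. That imputation is conditional (more than 5% missing, or a suspected mechanism), so state that it applies here regardless. Otherwise the complete-case rule could drop the record.
- State whether the modelled outcome is the on-treatment value or the change from baseline.

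In SAP 5.2, for run-in patients average the last run-in value, not screening, with the randomization value. State whether the average is arithmetic or on the log scale, and which period's baseline it replaces. Add the run-in urine to the collection list in SAP 4.1.

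The cost is SAP wording and slightly more programming. No new visit or sample is needed. A few week-12 baselines would be imputed instead of filled with a single value.

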3.2. Sample Size

Sample size calculations estimated 50 patients completing the study would provide 80% power to detect a 25% reduction in albuminuria. Assuming that approximately 5% of patients will discontinue the study prematurely, we intend to enrol 53 subjects. This calculation assumed a conservative standard deviation of 0.7 in log transformed proteinuria (within-subject standard deviation of 0.475) in order to detect (with alpha at 0.05) at least the 25% reduction in mean albuminuria (i.e, delta=0.288 on the log-transformed proteinuria scale) in dapagliflozin compared to placebo.

4. Study population

Male and female subjects with Chronic Kidney Disease aged between 18 and 75 years, proteinuria levels between 500 and 3500 mg/24-hour, and an eGFR ≥ 25 mL/min/1.73m² will be enrolled. Patients with type 1 or type 2 diabetes, polycystic kidney disease, glomerulonephritis with flares (lupus or anti-neutrophil cytoplasmic antibodies (ANCA) associated vasculitis) or ongoing active renal inflammation will be excluded. Patients have to be treated with a stable dose of an ACEi or ARB for at least 4 weeks prior to enrolment.

The study population will be selected from the outpatient clinical from hospitals based in the Netherlands (Groningen, Almelo, Amsterdam), Canada, (Toronto, Calgary, Vancouver) and Malaysia (Kuala Lumpur) with the following pre-specified inclusion and exclusion criteria.

Inclusion criteria

- Age ≥ 18 and ≤ 75 years
- Diagnosis of IgA nephropathy, focal segmental glomerulosclerosis, or membranous nephropathy. A biopsy proven diagnosis is not a prerequisite for participation in this study.
- Urinary protein excretion > 300 mg/g and ≤ 3500 mg/g in a 24-hr urine collection
- eGFR ≥ 25 mL/min/1.73m²
- On a stable dose of an ACEi or ARB for at least 4 weeks prior to randomization
- Willing to sign informed consent
- Women of Child-Bearing Potential (WOCBP):
 - WOCBP must be using an acceptable method of contraception to avoid pregnancy throughout the study and for up to 4 weeks after the last dose of study drug in such a manner that the risk of pregnancy is minimized.
 - WOCBP must have a negative serum or urine pregnancy test result (minimum sensitivity 25 IU/L or equivalent units of HCG) within 0 to 72 hours before the first dose of study drug.
 - Women must not be breast-feeding.

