5.3. Supplementary analyses

We will assess the change in primary and secondary outcomes during the dapagliflozin treatment periods with the change in proteinuria/albuminuria after stopping dapagliflozin;

This will be assessed by a longitudinal model as described above assessing the appropriate contrasts.

We will also assess the effect of dapagliflozin using 24-hr protein:creatinine ratio (and albumin:creatinine ratio as dependent variables. The model used for the primary outcome analysis will be used for this analysis.

Finally, the proportion of patients who achieve a proteinuria level <500 mg/g during follow-up will be summarized between dapagliflozin and placebo periods. Additionally, the proportion of patients with 30%, 40%, 50% reduction in proteinuria during follow-up will also be summarized between dapagliflozin and placebo group. McNemar and/or Mainland-Gart tests will be conducted depending on the nature of proportions and on the importance of the sequence order

Adherence on treatment, defined as pill count at least 80% during follow-up, will be summarized by treatment arm and study visits.

6. Evaluation of safety parameters

Counts and percentage per treatment arm will generally summarize all categorical indicators. A breakdown of SAEs stratified by fatal/non fatal status will be presented.

7. Proposed tables and figures

Table 1: Baseline characteristics for all randomised subjects by treatment group and in overall

Baseline Characteristics	Dapa (N=xxx)	Placebo (N=xxx)	Overall (N=xxx)
Categorical variables: n/N (%)			
XXX	xxx xxx	xxx xxx	xxx xxx
XXX	xxx xxx	xxx xxx	xxx xxx
XXX	xxx xxx	xxx xxx	xxx xxx
XXX	xxx xxx	xxx xxx	xxx xxx
Continuous variables:			
N Mean (SD)	xxx xxx xxx	xxx xxx xxx	xxx xxx xxx
Q1 Q2 Q3	xxx xxx xxx	xxx xxx xxx	xxx xxx xxx
min max	xxx xxx	xxx xxx	xxx xxx

Table 2: Baseline characteristics for all randomised subjects by group and by period

Baseline Characteristics	Group 1 Period 1 (N=xxx)	Group 1 Period 2 (N=xxx)	Group 2 Period 1 (N=xxx)	Group 2 Period 2 (N=xxx)
Categorical variables: n/N (%)				
XXX	XXX XXX	XXX XXX	XXX XXX	XXX XXX
XXX	XXX XXX	XXX XXX	XXX XXX	XXX XXX
XXX	XXX XXX	XXX XXX	XXX XXX	XXX XXX
XXX	XXX XXX	XXX XXX	XXX XXX	XXX XXX
Continuous variables:				
N Mean (SD)	XXX XXX XXX	XXX XXX XXX	XXX XXX XXX	XXX XXX XXX
Q1 Q2 Q3	XXX XXX XXX	XXX XXX XXX	XXX XXX XXX	XXX XXX XXX
min max	XXX XXX	XXX XXX	XXX XXX	XXX XXX

Table 3: Descriptive results of follow-up measurements by visits

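### The complementary analysis that adds weeks 3 and 15 has no term for correlation within a treatment period, so its pooled dapagliflozin-placebo standard error is too small whenever visits in the same period are correlated

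*SAP*

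**What the plan says.** SAP 5.1 analyses log 24-hour proteinuria with "treatment and period as fixed factor and patients (nested in sequence) as a random factor". It describes the model as two-level, with occasions within patients, and prints a general equation: an intercept made of a fixed mean and a patient effect, terms for treatment, period and their interaction, and one residual with a common variance. Protocol 9.1 and 9.2 likewise name patient as the only random factor.

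Later in SAP 5.1 comes the extension: "As a complementary analysis we will also include week 3 (mid-period 1 visit) and week 15 (mid-period 2 visit) data points". Its stated aim is to look for early treatment effects. It covers the primary outcome and those secondary outcomes that have mid-period data. No other covariance structure is named and no contrast is written out.

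SAP 5.3 compares changes during dapagliflozin with changes after stopping it: "This will be assessed by a longitudinal model as described above assessing the appropriate contrasts".

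SAP section 5 gives one rule for all tests: "All tests are to be two-sided with nominal level alpha set at 5" per cent. Neither document mentions a patient-by-period effect, a serial or unstructured covariance, or robust standard errors.

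**The concern.** In this design the unit that replicates the treatment comparison is the patient-period. With one value per period, a patient intercept captures all the correlation that matters. With weeks 3, 6, 15 and 18 in the model, the printed structure requires weeks 3 and 6 (same treatment, three weeks apart) to correlate no more than weeks 6 and 18 (different treatment, 12 weeks and a wash-out apart). Anything shared within a period, such as diet, background therapy or disease activity, is then counted as fresh replication.

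The result would be short intervals and small p-values in an analysis likely to be read as support for the primary result. The outcomes reached are proteinuria, albuminuria, body weight and systolic pressure. Measured GFR has no week 3 or 15 visit in the protocol's time and events table, and SAP 5.1 itself excludes eGFR.

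**Working it through.** **The plan's own figure.** Protocol 3.4 states that "50 patients completing the study will provide 80% power to detect a 25% reduction in albuminuria", with "delta=0.288 on the log-transformed proteinuria scale" (SAP 3.2) and an SD of 0.7, using a paired t-test. Reading 0.7 as the SD of the paired difference, the noncentral t calculation gives 81.4% power at n=50, and n=49 for 80%. Enrolment is 50/0.95 = 52.6, so 53. The sample size reproduces. It rests on one value per treatment per patient, so nothing below affects it.

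**Inputs for the check.** 50 patients, 25 per sequence (assumed balanced), within-patient SD 0.475 (Protocol 3.4), two-sided 5%. The share r is not in the documents, so a range is shown. The SD cancels from every ratio.

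**Pooled treatment effect, values as outcome.** Set the within-patient variance to 1 = r (shared by the visits of a period) + (1−r) (specific to the visit).

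- Variance of a two-visit period mean: r + (1−r)/2 = (1+r)/2.
- True variance of a patient's treatment difference: 2 × (1+r)/2 = 1+r.
- Each patient gives three within-patient degrees of freedom: one between periods, with mean square 1+r, and two within periods, with mean square 1−r. The expected residual mean square is [(1+r) + 2(1−r)]/3 = (3−r)/3. The intercept-only model uses this as the variance of the same difference.
- Model SE / true SE = sqrt[(3−r)/(3(1+r))]. Type I error ≈ 2Φ(−1.96 × ratio).

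| r | ratio | type I error |
|---|---|---|
| 0 | 1.00 | 5% |
| 0.1 | sqrt(2.9/3.3) = 0.94 | 6.6% |
| 0.3 | sqrt(2.7/3.9) = 0.83 | 10.3% |
| 0.5 | sqrt(2.5/4.5) = 0.75 | 14.4% |

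Simulation (8,000 trials per value) gave 4.9%, 9.4% and 14.7% at r = 0, 0.25 and 0.5 with the patient intercept only. With a patient-by-period effect it gave 4.9%, 5.1% and 5.2%. AR(1) errors with a three-week correlation of 0.3 to 0.7 gave ratios of 0.83 to 0.70 and type I errors of 10% to 17%, so the finding does not depend on one form of correlation.

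**Pooled effect, change from each period's own baseline.** SAP Tables 6 and 7 report change from baseline in each period, and Table 2 lists baselines by period. Even at r=0, each change has variance 1+1 = 2, of which 1 comes from the baseline that weeks 3 and 6 share. The shared fraction is 1/2, so the formula applies with 0.5 in place of r: a ratio of about 0.74 (0.741 with 50 patients) and a type I error of about 14%. If week 0 served as baseline for both periods, it would be a patient constant absorbed by the intercept, and the table above would apply instead.

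**Week 3 tested alone, with visit terms.** The true variance of a patient's difference is 2 and the model uses 2(3−r)/3. The ratio is sqrt[(3−r)/3]: 0.95 at r=0.3 and 0.91 at r=0.5, with type I errors of 6.3% and 7.4%.

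**SAP 5.3 contrasts, weeks 0, 6, 12, 18 and 24.** Of the 10 visit pairs, two lie in the same period (0/6 and 12/18), so the residual mean square is 1 − 0.2r.

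- On-drug change, week 0 to 6: the shared effect cancels and the true variance is 2(1−r). The ratio is sqrt[(1−0.2r)/(1−r)] = 1.12, 1.34 and 1.84 at r = 0.25, 0.5 and 0.75.
- Change after stopping, week 6 to 12: the true variance is 2. The ratio is sqrt(1−0.2r) = 0.97, 0.95 and 0.92.

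With weeks 3 and 15 also included, or with AR(1) errors, the on-drug ratio stays above 1 (down to 1.01). Across these cases the after-stopping ratio runs from 0.89 to 1.17.

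**The case against.** The strongest reply has four parts.

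*The analysis is exploratory and non-primary.* This is correct. Nothing in the SAP lets it override the week 6/18 comparison, and that limits the severity.

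*The aim is an early effect, which points to a week 3 test rather than a pooled one.* This is fair. On that reading the inflation is small (6.3% to 7.4%). But no contrast is written, and the printed model has no visit term, so following it literally gives the pooled effect.

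*The size rests on r, which nobody has stated.* This is also true. With raw values and r=0 there is no error at all. It does not rescue the plan: the model is valid for values only at r=0, and change from a period-specific baseline brings in shared variance without any assumption about r.

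*The model already accounts for repeated measures.* It does so through the patient intercept. A reader might infer that visits are treated as fully independent; they are independent only given the patient.

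A reader might also infer that error bars are too narrow in SAP 5.3, since it borrows the same model. The check does not support that. The on-drug change tends to get a standard error that is too wide, and the after-stopping change can be off modestly in either direction.

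**Conclusion.** The point holds for the SAP 5.1 complementary analysis. As printed, the model understates the standard error of the pooled dapagliflozin-placebo effect whenever visits in a period share variance. For values, the ratio is 0.94 to 0.75 for r from 0.1 to 0.5, with type I error of about 6.6% to 14%. For change from each period's own baseline, it is about 0.74 and 14% even at r=0. These figures assume 25 patients per sequence, complete data and two on-treatment visits per period; r itself is an assumption.

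In SAP 5.3 the covariance is misspecified too, but no claim of uniformly narrow intervals is justified there. It would also be wrong to read this as a doubt about the primary result or about the 50 completers. Minor: a non-primary analysis with a cheap remedy.

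**What to change.** In the SAP 5.1 complementary analysis, add a random patient-by-period effect to the printed model, or use an unstructured within-patient covariance over weeks 3, 6, 15 and 18 (4×5/2 = 10 parameters). State whether values or changes are modelled, which visit is the baseline in period 2, and whether the target is the pooled effect or the week 3 effect. Keep the single patient intercept for the primary model with one value per period.

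The cost is a sentence in the SAP and one extra RANDOM or REPEATED statement, with no new data. Intervals for the pooled effect on values widen by the reciprocal of the ratio: about 7% at r=0.1, 20% at r=0.3 and 34% at r=0.5.

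SAP 5.3 needs a little more. Write out the contrasts first, then use a covariance that allows for serial or within-period correlation (AR(1) or spatial power, for example) or robust standard errors. A patient-by-period effect is awkward there, because week 12 both ends the first wash-out and opens period 2, and week 24 follows both treatment periods. An unstructured matrix over seven visits would need 7×8/2 = 28 parameters from about 50 patients.
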